Patients and study coordinators will enter baseline demographic, gout history, patient reported outcomes (PROs) directly into electronic case report forms into a 21CFR and HIPAA compliant REDCap (Nashville, Tennessee) system. We will host REDCap on one of several access-controlled, encrypted servers housed at UAB. Subsequent PROs and other outcome data will be captured by phone in the same REDCap database by the study teams. Baseline laboratory data and medication data will be obtained from our respective EMRs and will be reviewed during the phone calls and by the research assistant during the ED visit.

B.8 Study Outcomes

Study outcomes (**Table 2**) will be collected from patients at 6 weeks and 3 months following the initial ED visit with questionnaires deployed using computer assisted telephone interviews (CATI) programmed in REDCap. Validated items about gout flares and gout medications have been used in the past by our team.⁸⁴

B.8.1 Primary outcomes Aim 1 and 2.

The primary outcome of aim 1 will be the ability of the alert to successfully identify gout patients. For aim 2, it will be the proportion of patients that have a follow-up visit addressing gout in the 3-month period after the ED visit. Many gout patients are not adherent with their follow-up visits due to a lack of awareness of the consequences of untreated

gout, poor care access, and/or inadequate assistance to obtain a follow up visit. Even rapidly-scheduled outpatient visits (next business day) following an ED encounter are only attended by 73% of those seen in a recent study and rates of post-ED follow-up for many chronic disease are closer to 50%.^{91, 92} Moreover, most patients, ~80%, leave the ED with knowledge deficits that impact adherence and outcomes.^{93, 94} Having a usual source of primary care and establishing continuity of care after an ED visit is critical to optimal disease outcomes in all chronic diseases including gout.³⁰⁻³² This data will be captured both by self-report on surveys (this will be the primary study outcome) and by review of EMR data within our respective healthcare systems. While self-report will be impacted by recall and possible social desirability bias, this should be non-differential (bias towards the null).⁹⁵ EMR data will be more accurate for some outcomes but will miss any gout care delivered outside our urban Southeastern medical centers and their satellite facilities.

B.8.1.1 Secondary outcomes - Aim 2

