The navigator will conduct two additional follow-up calls at approximately one month (4 weeks) and in the week (anticipated) prior to their visit to confirm the appointment time, the level of support needed (as needs may have changed), and encourage him/her to keep their appointment. In the unlikely event that the appointment with the PCP/gout specialist is sooner than one month, this one-month pre-appointment call will be eliminated and the navigator will have only two calls with the patient.

B.9.1.3 *6 Week Follow-up Assessment*

At 6 weeks following ED visit, participants will be contacted by the Coordinating Center (CC) to to assess project outcomes via a telephone survey. The following information will be collected, and data collected via the surveys and EMR. Following completion of the follow-up surveys the study coordinator will inform and debrief the patient that they participated in a study evaluating methods to improve continuity of gout care. The debrief will be conducted after the 1st survey. If RA the coordinator is unable to reach participant on the phone, the survey questions used to collect the primary outcomes will be sent via email or text messaging using Mosio, which is an HIPAA-compliant application.

- Survey assessments
 - Patient satisfaction
 - HRQL
 - PROs
- Updated medical history and review of concomitant medications
- Assessment of Adverse Events (AEs) (as meeting NIH definition of Phase III study AEs will be collected)

B.9.1.4 *3 Month Follow-up Assessment*

At 3 months (anticipated) post ED visit participants will be contacted to complete a second follow-up survey and end of study (EOS) via telephone to assess secondary outcomes (e.g. adherence to orders, medication RX, and labs (if ordered)).

- Survey assessments
 - Patient satisfaction
 - HRQL
 - PROs
- Updated medical history and review of concomitant medications
- Assessment of Adverse Events (AEs) (as meeting NIH definition of Phase III study AEs will be collected)

B.9.1.5 **Table 1 Visit Schedule**

Visit description / Study procedures	Screening and Enrollment (ED)	V1 (phone)	V2 (phone)	V3	V4 EOS
	Day 0	72 Hours	4 WK	6 WK [°]	3 MO
Review of Inclusion/exclusion criteria following alert notification	X				
Informed consent for INSIGHT Registry	X				
Medical history	X				
Laboratory					
SUA	X				
Sample banking	X				
Randomization	X				
Patient Navigator Contact#		X	X ^{\$}	X ^{\$}	
Updated medical history and concomitant medications		X	X	X	X

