Outcome ascertainment	X			X	X
Study debriefing				X	
Assess AEs			X	X	X

[°]Primary outcome assessment will occur at any point upto 6 weeks post ED visit dependent on routine care visit; # For individuals randomized to navigation arm; ^{\$}Navigator will contact participant in the week prior to scheduled follow-up visit

B.9.1.6 **Blinding and Unblinding**

Participants will blinded to study assignment at enrollment, and following primary outcome ascertainment will be debriefed regarding the study and its purpose/goals.

B.10 Statistical Analysis Plan

B.10.1 Primary Outcome Analysis - Aim 1.

All analyses will adhere to the principles of rigor, reproducibility and transparency.^{109, 110} To determine the effectiveness of our alert system, we will examine the diagnostic properties (sensitivity/specificity) of the EMR alerts against a gold standard of NLP/ML detection (section C.4.2)

B.10.2 Primary Outcome Analysis- Aim 2.

Descriptive statistics, including measures of central tendency (means for continuous, proportions for categorical) and dispersion (variance, interquartile range) will summarize the distribution of baseline characteristics of randomized patients seen in both EDs. Descriptive statistics will be summarized by treatment arm as well as enrollment site. These statistics will inform the successfulness of randomization in creating comparable groups and ascertain our success in recruiting the populations we seek to target (particularly under-represented minorities). We also will compare the descriptive characteristics between those participants who do and don't respond to follow-up surveys to detect and report any evidence of a selective non-response bias. The primary analysis approach for testing treatment effect will be a multivariable logistic regression

model. We have chosen multivariable logistic regression over Cochran-Mantel-Haenszel approaches to allow for effect estimation of multiple covariates (race, gender, age) upon the primary outcome and to allow tests of interactions. Logistic regression models, including interaction terms, will be developed for 6 week outcomes and 3 month outcomes. We will examine the significance of the effects of the intervention as the outcome of persons receiving at least one outpatient gout follow-up visit at 3 months. We will analyze rates on an intent-to-treat basis for the primary analysis. We will conduct all analyses using SAS 9.4 (Cary, NC)

[figure not shown]

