Investigational study sites are the University of Alabama at Birmingham and Vanderbilt University Medical center, two large academic medical centers. The study site staff will ensure participants are consented and randomized in accordance with established good clinical research practices. Additionally, site investigators and their staff will be required to have prerequisite human subjects training, and will answer study related questions, as needed.

- University of Alabama at Birmingham (UAB), Birmingham, AL, United States
- Massachusetts General Hospital (MGH), Boston, MA, United States
- MetroHealth Medical Center, Cleveland, OH, United States
- University of Iowa, Iowa City, IA, United States

Approximately n= 168 participants will be enrolled at the UAB site and n = 112 from MGH, MetroHealth, and University of Iowa study sites.

D.1 Participant Recruitment and Consent

The site study staff will:

- Provide participants with adequate information concerning the study procedures, and scope
- Provide adequate opportunity for the participant to consider all available options
- Respond to the participant's questions and concerns
- Ensure that each participant understands all information provided
- Obtain the participant's written voluntary consent to participate
- Sign the consent form as witnesses
- Provide participants with a copy of the consent form

D.2 Participant Retention/Discontinuation

Participants will have the option to withdraw from the study at any time. Study staff will make at least 3 attempts to contact participants for study intervention visits (ie, Patient Navigation at UAB, MGH, MetroHealth,

and University of Iowa) and outcomes assessment surveys at 6 weeks and 3 months. In order to minimize the chances of losing touch with patients, study staff are collecting email addresses and secondary contact names and phone numbers at the original emergency department visit.

If study staff are not able to reach participants after at least 3 phone attempts, they will attempt to reach the secondary contact listed and/or send an email or text message to the participant. Text messages will be sent through the Mosio application, which is an HIPAA-compliant application. If these methods are not successful in contacting participant, then participant will be considered lost to follow up.

D.3 Site Monitoring

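### The primary outcome is a telephone self-report, but nothing requires outcome callers to be masked to arm, and participant blinding ends before the 3-month endpoint

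*Combined protocol and SAP*

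**What the plan says.** **Outcome and its source.** B.8.1 defines the Aim 2 primary outcome as the proportion of patients with a visit addressing gout in the 3 months after the ED visit. It states: "This data will be captured both by self-report on surveys (this will be the primary study outcome". EMR review is the second source, and B.8.1 concedes that it misses gout care outside the participating systems. B.8 says outcomes are collected at 6 weeks and 3 months by "questionnaires deployed using computer assisted telephone interviews (CATI) programmed in REDCap".

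**Blinding.** B.9.1.6 is one sentence: "Participants will blinded to study assignment at enrollment, and following primary outcome ascertainment will be debriefed" about the study's purpose. No section mentions masking of interviewers, coordinators or analysts.

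**Who calls.**
- Intervention calls: lay patient navigators (B.5.2, B.9.1.2).
- 6-week survey: "participants will be contacted by the Coordinating Center (CC" (B.9.1.3). The same paragraph refers to the RA or coordinator failing to reach the participant by phone.
- 3-month survey: no caller named (B.9.1.4).
- In general: "Subsequent PROs and other outcome data will be captured by phone in the same REDCap database by the study teams" (B.7).
- Retention: "Study staff will make at least 3 attempts to contact participants for study intervention visits", and D.2 uses the same subject for the outcome surveys.
- Randomization: the research assistant in the ED (B.5.1).

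**Reporting bias.** B.8.1: "While self-report will be impacted by recall and possible social desirability bias, this should be non-differential (bias towards the null".

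**Debrief.** B.9.1.3 and the visit schedule in B.9.1.5 place it after the 6-week survey.

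**The concern.** A binary self-report taken by telephone can be shaped by the person asking and by the person answering. Here both may depend on arm.

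On the asking side, no text prevents a caller who knows the allocation from collecting the primary outcome. On the answering side, the intervention videos stress follow-up care for gout (B.5.2) and navigators encourage patients to keep that appointment. Controls receive a usual-care referral and preventive-health material unrelated to gout (B.5.3). Social desirability could therefore differ between arms, and over-reporting concentrated in the intervention arm biases away from the null. The plan assumes the opposite direction without giving a reason.

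At stake is whether a positive primary result can be read as more visits rather than as more reported visits.

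**Working it through.** **1. Is masking or separation required anywhere?** Setting the sections side by side:

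| Contact | Who, per the plan | Masked to arm? |
|---|---|---|
| Randomization in the ED | ED research assistant (B.5.1) | No: carries out the allocation |
| Navigator calls | Lay navigators (B.5.2, B.9.1.2) | No: they deliver the intervention |
| 6-week survey | Coordinating Center; RA/coordinator also mentioned (B.9.1.3) | Not stated |
| 3-month survey | Not named (B.9.1.4); study teams in general (B.7) | Not stated |

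Roles are partly assigned. Nothing excludes arm-aware staff from outcome contact, and the call that closes the 3-month window has no named caller.

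**2. Does participant blinding last to the endpoint?** The debrief follows the 6-week survey, but the endpoint runs to 3 months (B.8.1, B.10.2). On that definition, participants learn the study's purpose before the outcome is complete. The footnote to the visit schedule in B.9.1.5 puts primary assessment at any point up to 6 weeks, and B.9.1.4 describes the 3-month call as assessing secondary outcomes. These statements need to be reconciled with B.8.1.

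**3. The plan's own power figure.** Inputs from B.11: N = 200 at 2:1 (66.7 control, 133.3 intervention), control rate 30%, RR 1.68 (0.30 × 1.68 = 50.4%), two-sided alpha 0.05.
- Pooled rate = (66.7 × 0.30 + 133.3 × 0.504)/200 = 0.436.
- SE under the null = √[0.436 × 0.564 × (1/66.7 + 1/133.3)] = 0.0744.
- SE under the alternative = √[0.30 × 0.70/66.7 + 0.504 × 0.496/133.3] = 0.0709.
- Power = Φ[(0.204 − 1.96 × 0.0744)/0.0709] = Φ(0.82) = 79.4%, against the stated 80%. It reproduces.

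**4. Illustration of differential misreporting.** Evaluable patients: 280 × 0.70 = 196, or 65 control and 131 intervention at 2:1. Assume the same true visit rate in both arms, accurate reporting by controls, and an intervention-arm reported rate raised by e points. The documents give no value for e. With the same test, the two-sided rejection probability is Φ[(e − 1.96·SE₀)/SE₁] + Φ[(−e − 1.96·SE₀)/SE₁].

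For e = 0.05 at a 30% rate: pooled rate = (65 × 0.30 + 131 × 0.35)/196 = 0.333; SE₀ = 0.0715; SE₁ = 0.0705. The terms are Φ(−1.28) = 10.0% and Φ(−2.70) = 0.35%, which sum to 10.4%.

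| e (assumed) | True rate 30% | True rate 50% |
|---|---|---|
| 0 | 5.0% | 5.0% |
| 3 points | 6.9% | 6.8% |
| 5 points | 10.4% | 10.1% |
| 10 points | 27.2% | 26.5% |

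The rates include rejections in the wrong direction: at 3 points and a 30% rate, 6.1% favour the intervention and 0.8% favour control. At a 30% rate, 10 points means 10/70, or about 14%, of intervention-arm non-visitors recorded as having a visit. The test approximates the logistic model in B.10.2.

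**The case against.** The strongest reply is that the plan already separates roles and limits interviewer discretion. Navigators make the intervention calls and the Coordinating Center makes the 6-week call. Questionnaires are programmed, the email or text fallback has no interviewer, controls get attention-control material, both arms get a referral, and EMR visits are reviewed as a second source. D.3 also refers to a manual of procedures, not among these documents, which could set call assignment.

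Much of this stands, and it rules out several stronger readings:
- From D.2 a reader might infer that the same people make intervention and outcome calls. D.2 concerns the number of contact attempts and uses a generic term; the sections that assign roles name different callers.
- A reader might take B.9.1.6 to leave interviewers unblinded by design. It is silent on them.
- A reader might suppose that the survey question calls for interviewer judgement. The documents do not give its wording.
- A reader might take the rejection rates as the effect of unmasked interviewers. They show sensitivity to differential misreporting from any cause, and nothing in the documents shows that such misreporting occurs.

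It is also true that masking callers cannot stop a participant who was encouraged to attend from over-reporting. That calls for a check against another source as well as masking.

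The reply does not close the gap. The 3-month caller is unnamed, RA contact is contemplated, no masking is stated, and no analysis of the primary outcome using EMR visits is specified. The only sensitivity analysis named is multiple imputation for missing data (B.10.3).

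**Conclusion.** The point holds as a gap in specification. The plan does not require outcome callers to be masked to arm or separate from arm-aware staff, so its statement that self-report bias is non-differential has no support. On the 3-month definition of the endpoint, participant blinding, the only blinding planned, ends early.

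The size of any bias is unknown. Under the assumed 3 to 10 points of intervention-arm over-reporting, with accurate control reports, no true effect, a 30% visit rate and non-response equal across arms, a nominal 5% test rejects in 6.9% to 27.2% of trials. B.11 itself expects non-response to differ slightly by arm. The share of such misreporting that interviewer masking would remove cannot be estimated from the documents. The change is worth making because it protects the primary endpoint at little cost.

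**What to change.** - **B.9.1.6, B.9.1.3 and B.9.1.4:** state that both the 6-week and 3-month telephone surveys are done by Coordinating Center staff who are neither navigators nor the randomizing research assistant. Hide arm and navigator fields from them by REDCap user rights, use a fixed script, and record any unmasking.
- **Debrief:** move it to after the 3-month primary outcome question, and reconcile the B.9.1.5 footnote and B.9.1.4 with the 3-month definition in B.8.1.
- **B.8.1:** remove the assurance that self-report bias is non-differential.
- **B.10.2:** add a sensitivity analysis of the primary outcome using the EMR visit data already planned. State that it misses outside care, so a reported visit absent from the EMR is not proof of over-reporting.

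**Cost:** a permission setting, call assignment, a script change and a protocol amendment. The Coordinating Center already makes the 6-week call, so no new staff should be needed; who now makes the 3-month call must be settled in any case. The sample size does not change. The downside is that some participants will reveal their arm during the call.

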The NLP algorithm to create the gout alert in the EMR will be structured and refined with serial pilot testing and chart validation (see B.3.2) initially in the Cerner environment at UAB. We will annotate a set of ED triage chief complaint notes and problem lists for the presence of gout flares and implement a simple algorithm for gout flare ED alerts. The keywords will be used to identify gout patients in the ED possibly experiencing a flare. Patients with a potential acute gout flare will be identified using structured data elements (e.g. prior ICD code for gout) and keywords such as: "gout," "podagra," "monoarthritis," "toe pain" from all data fields in the EMR. These terms shown in Table 1 will be developed as part of the alert development and NLP algorithm. The alert algorithm will be developed iteratively using a gout enriched data cohort until acceptable performance is achieved. Keywords will be normalized using NLP to identify gout patients in the ED possibly experiencing a flare. The algorithm will work on simple Boolean logic and regular expressions and will identify a gout flare based on the presence of a gout keyword to the left of any of the PMH-GAZETEER words OR if there is both a location from the LOCATION-GAZETEER and the gout keyword in the past medical history.

Table 1. Example Description Terms and Gazeteer

GOUT-GAZETEER Case Insensitive	LOCATION-GAZETEER Case Insensitive	LOCATION-GAZETEER Case Sensitive	PMH-GAZETEER Case Insensitive
Gout	toe	knee	LLE
Pain	ankle	wrist	RLE
Tender	foot	feet	LUE
Swelling	thumb	finger	RUE
Swollen	arm	elbow	UE
Stiff	shoulder	hip	LE

The alert algorithm will be developed iteratively in the Cerner environment until acceptable performance achieved. Once acceptable performance is achieved the keywords used and any rules will be provided to other sites as they are identified and approved by the UAB IRB for deployment in the their EHR environments.

B.3.2 Alert Chart Validation

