An alert development dataset will be created by identifying patients at UAB with an ED visit starting in January 2020 and working back until sample size is met. A random sample of 100 charts with an ICD10 code for gout and 50 charts with no ICD10 code for gout (but for whom the alert was triggered) will be identified and reviewed by two trained abstractionists. Data abstraction will look to confirm: 1) a prior history of gout and 2) a gout flare during the time of the ED visit diagnosis; or 3) other potential diagnosis. The review will include past clinic notes for documentation of a diagnosis and clinical features of gout (based on 2015 ACR/EULAR classification criteria for gout), medication lists for drugs used for treatment of gout, review of laboratory and

other diagnostic tests (serum urate and joint fluid urate results), imaging studies consistent with gout diagnosis and management (joint radiographs, ultrasound and CT/MRI) and detailed review of the ED visit to confirm acute gout flare at that time. The abstraction form will be piloted before implementation, and necessary changes will be made. Following abstraction of chart data elements and compilation of the 150 patient dataset by the physician trained research coordinators, two expert rheumatologists will complete a diagnosis confirmation review. In the event there is discordance a third rheumatology clinician will serve as an adjudicator.

B.4 Video Intervention Development

In order to develop the video intervention, a group of patients who are currently successfully managing their gout will be interviewed and asked to tell their stories about the importance of gout care. The overall goal of the gout interviews is to improve patient gout knowledge and encourage actions that will prevent flares, destigmatize gout, and enhance readiness to adopt available long-term treatments including medications, diet, and exercise. Interviews will be conducted to cover a variety of race/ethnicities that might be seen in the ED with gout. Videos will be compiled from these patient interviews as anecdotes taken from these gout patients and presented to people in the ED who are being seen for a potential gout flare. These videos will seek to motivate participants to seek further gout care from their primary physician and the importance of taking ULT medications post-ED discharge.

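### The Aim 1 analysis scores the alert against NLP/ML detection under a section number that does not exist, instead of the rheumatologist review in B.3.2, and it names no dataset

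*Combined protocol and SAP*

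**What the plan says.** B.10.1 is the only analysis text for Aim 1: "we will examine the diagnostic properties (sensitivity/specificity) of the EMR alerts against a gold standard of NLP/ML detection (section C.4.2". It names no dataset.

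B.3.1 describes how the alert is made: "NLP algorithm to create the gout alert in the EMR will be structured and refined with serial pilot testing and chart validation (see B.3.2". Its inputs include "structured data elements (e.g. prior ICD code for gout", together with keywords. B.3.1 also says "We will annotate a set of ED triage chief complaint notes and problem lists for the presence of gout flares", and refers to a cohort enriched for gout. It does not say how either set is sampled, or whether they are the same set.

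B.3.2, headed Alert Chart Validation, begins "An alert development dataset will be created by identifying patients at UAB with an ED visit". The charts are 100 sampled at random with an ICD10 gout code and "50 charts with no ICD10 code for gout (but for whom the alert was triggered". On content: "Data abstraction will look to confirm: 1) a prior history of gout and 2) a gout flare during the time of the ED visit". After "compilation of the 150 patient dataset", two rheumatologists confirm the diagnosis and a third adjudicates disagreements. B.10.1 mentions none of this.

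The target condition also varies. A.2 speaks of acute gout flares, while B.8.1 defines the Aim 1 primary outcome as identifying gout patients.

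**The concern.** A diagnostic accuracy analysis needs a reference standard that is independent of the test and closer to the truth than the test. NLP detection is neither when an NLP algorithm produces the alert. If the same algorithm is meant, the comparison is circular. If a separate NLP/ML process is meant, the documents do not describe it, and the result would be agreement between two tools. Either way, the declared Aim 1 primary outcome would not be measured against a clinical diagnosis, although the review that could supply one is already planned.

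Two further points arise if the B.3.2 charts are the intended data. The 50 uncoded charts were selected on the test result itself, so they carry no information on missed flares. The charts are also called a development dataset, and B.3.1 ties refinement of the algorithm to B.3.2, so figures from charts used for tuning would describe apparent performance.

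**Working it through.** **Step 1: the pointer.** Section C is Adverse Events and has no numbered subsections. B.11 cites C.3.5 and C.4.4, which do not exist either. Leftover section numbers are the likely cause. Correcting the number would still leave NLP/ML detection as the stated standard.

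**Step 2: what the 150 charts can show.** The plan's total reproduces: 100 + 50 = 150. By sampling group, for the alert version that selected the charts:

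| Group | Alert positive | Alert negative | Estimable |
|---|---|---|---|
| Coded, 100 charts | sampled | sampled | sensitivity and specificity within the group, once alert status is assigned |
| Uncoded, 50 charts | all 50 | none | PPV only |

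A prior gout code is one of the alert's inputs, so accuracy in coded charts may not carry over to uncoded visits. B.3.2 does not say whether its code is a prior code or one from the index visit.

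**Step 3: precision within groups.** Assumptions, not document figures: 50 to 90 of the 100 coded charts are flares; sensitivity and specificity are both 80% there; PPV is 30% in the uncoded charts. Wilson 95% interval, with z = 1.96: [p + z²/2n ± z√(p(1−p)/n + z²/4n²)] / (1 + z²/n).

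- Sensitivity: 40/50 gives 67-89%; 72/90 gives 71-87%.
- Specificity: 40/50 gives 67-89%; 8/10 gives 49-94%.
- PPV: 15/50 gives 19-44%.

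**Step 4: pooling, for the selecting version only.** Let F be the flares among coded charts, N = 100 − F, and v the PPV in the 50 uncoded charts. Pooled sensitivity = (0.8F + 50v)/(F + 50v). Pooled specificity = 0.8N/(N + 50(1 − v)).

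| F | v | Sensitivity | Specificity |
|---|---|---|---|
| 50 | 0.1 | 45/55 = 82% | 40/95 = 42% |
| 50 | 0.3 | 55/65 = 85% | 40/85 = 47% |
| 50 | 0.5 | 65/75 = 87% | 40/75 = 53% |
| 90 | 0.1 | 77/95 = 81% | 8/55 = 15% |
| 90 | 0.3 | 87/105 = 83% | 8/45 = 18% |
| 90 | 0.5 | 97/115 = 84% | 8/35 = 23% |

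With 60% sensitivity in the coded charts and F = 50, pooled sensitivity is 35/55 = 64% to 55/75 = 73%, and specificity is again 42-53%.

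**Step 5: a refined alert.** A later version need not fire on all 50 charts. Take F = 50 and v = 0.3, so 15 flares and 35 non-flares are uncoded. If refinement silences 30 of the 35 and 8 of the 15, pooled specificity is (40 + 30)/85 = 82% and pooled sensitivity is (40 + 7)/65 = 72%. Against 80%, both shifts reverse.

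**Step 6: overall sensitivity.** Assume 1,170 coded visits a year (720 + 450 gout patients in B.11, treated as visits), half of them flares, 60% sensitivity (B.11's expected capture rate, used as a stand-in), and 300 uncoded alerts with PPV 30%. Detected flares are 1,170 × 0.5 × 0.6 + 300 × 0.3 = 441. Missed flares are 1,170 × 0.5 × 0.4 + M = 234 + M, where M counts flares in uncoded visits without an alert. Sensitivity is 441/675 = 65% at M = 0, 441/775 = 57% at M = 100, 441/975 = 45% at M = 300 and 441/1,275 = 35% at M = 600. The 150 charts look the same in every case.

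Overall specificity hardly depends on M. Assume also 80% specificity in coded visits and 50,000 ED visits. False alerts are 1,170 × 0.5 × 0.2 + 300 × 0.7 = 327. At M = 0 the non-flare visits number 50,000 − 675 = 49,325, so specificity is 48,998/49,325 = 99.3%. This needs visit and alert counts that the 150 charts do not contain.

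**The case against.** The strongest reply is that one unclear sentence is being read too literally. B.3 is headed as alert development and validation for Aim 1, and B.3.2 as alert chart validation with rheumatologist review, so the team may well mean that review. This is plausible. A reader might infer that the plan has no clinical reference standard at all, and the documents do not support that. The review exists; B.10.1 fails to use it and names something else. A SAP should not leave the primary reference standard to be guessed.

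The second reply is that nothing assigns the 150 charts to B.10.1, since B.3.1 also mentions annotated notes and an enriched cohort. This stands, so every statement here about the charts is conditional on their being the dataset, and the apparent-performance label applies only where charts were used for tuning.

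Third, a reader might infer that the plan will pool the charts, or that pooling must always inflate sensitivity and depress specificity. Neither is supported. Compiling one dataset for review is not a pooled two-by-two table, and Step 5 shows that the direction can reverse for a refined alert.

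Fourth, weighting could recover more. With recorded counts of visits and alerts, overall PPV could be obtained and overall specificity approximated. That is correct, but the plan describes neither counts nor weights, and overall sensitivity would remain out of reach.

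**Conclusion.** The concern holds, and it should be fixed. The stated reference standard for the Aim 1 primary analysis is wrong as written: the cited section does not exist, and the named method is of the kind that builds the alert. This rests on the text alone, with no numerical assumption.

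The dataset part is conditional. If the 150 charts are used, they give sensitivity and specificity within the coded charts, PPV in the uncoded charts for the version that selected them, and no overall ED sensitivity. Overall specificity cannot come from the charts alone. The pooled ranges (sensitivity 81-87%, specificity 15-53%) illustrate an analysis that the plan does not state, under assumed inputs and for the selecting version only; they are not predictions.

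A reader might also infer that the trial's treatment comparison is weakened. It is not. Under B.2, entry to Aim 2 rests on clinical flare criteria or the ED physician's diagnosis, not on the alert's accuracy.

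**What to change.** In B.10.1:

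- Name the rheumatologist-adjudicated diagnosis of B.3.2 as the reference standard and correct the pointer to B.3.2.
- State the target condition, acute flare or gout, and the dataset. If the annotated notes of B.3.1 are used, state how they are sampled.
- Report any NLP/ML comparison as agreement, not accuracy.

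If the 150 charts are the dataset:

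- Run the alert retrospectively on the 100 coded charts and report sensitivity and specificity within that group, with 95% CIs.
- For the version that selected the 50 uncoded charts, report only PPV there, with a 95% CI, and do not pool the groups.
- If a refined version is scored, rerun it on those 50 and state that they were sampled on an earlier alert version's status.
- Do not claim overall ED sensitivity. Give overall specificity only as an approximation, and only with recorded visit and alert counts and stated weights.
- Label figures from any charts used for tuning as apparent performance.

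The cost is wording plus a small alert run, since alert status is not among the abstraction items listed in B.3.2. Charts and reviewers stay the same. The downside is a narrower accuracy claim, with imprecise specificity if few coded charts are non-flares.
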